5.1. Pre-registration evaluation

Recruitment

Primary prevention patients with a moderate ASCVD risk.

5.2. Inclusion criteria

1. Over 40
2. Moderate ASCVD risk
3. Decline statin therapy

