1.1. Study summary

Design

Patients will be randomized to receive either 30mg of atorvastatin or be presented with a choice of receiving either a “natural” statin (red yeast rice extract) or 30mg of atorvastatin.

In the intervention arm, a goal of either LDL-C reduction of at least 50% or an LDL-C < 100 mg/dl will be discussed on the initial visit. Goals will be re-assessed at 2 months, if goals are not met, patients will be given 30mg of atorvastatin.

Aims

To assess if introducing greater patient autonomy increases patient compliance with statin therapy.

Outcome measures

The primary endpoint will be 6-month compliance of statin therapy, after the initiation of atorvastatin.

Secondary endpoints will be rates of perceived side effects from statin use, including myalgias, fatigue, mental fog and GI upset.

Population

This will be a multi-center study of 300 pts, 150 in each arm.

Eligibility

Primary prevention (no history of CAD, MI, or stroke) patients with a moderate 10-year ASCVD risk who decline statin therapy.

Duration

Anticipated recruitment is 6 months. Follow-up will be performed at 6 months in the control arm and 2 and 8 months in the intervention arm, for a total study duration of 14 months.

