1.1. Study overview diagram

4.2 Study protocol:

Patients meeting the study criteria will be enrolled at outpatient cardiology clinics at four centers: Lithuanian University of Health Sciences, Northway Medical Centre, Prienu Hospital, and Unomeda Medical Centre. The enrolment period will last six months, with an estimated 50 patients per month enrolled into the study, for a total of 300 patients.

Patients will be randomized to either the control group or the intervention group. Baseline variables will include demographic variables (age, gender, BMI, blood pressure, heart rate), medical history (hypertension, hyperlipidaemia, type 2 diabetes mellitus, tobacco use), laboratory variables (total cholesterol, HDL, LDL, triglycerides, AST, ALT, creatine kinase, and, vitamin D levels) and socioeconomic variables (education level, income level, rural or urban, and marriage status).

The control group will be provided reassurance through a short, semi-structured discussion on the excellent safety profile of statins, similar to a typical interaction between a clinician and patient. They will then be prescribed 30mg atorvastatin daily as a 30 tablets supply with five patient-initiated re-fills for 30 tablets each. Final follow-up in this group will occur at 6 months.

The intervention group will be offered a red yeast rice extract 20mg nightly to achieve a goal LDL-cholesterol of <2.6 mmol/L (100 mg/dL) in accordance with the 2019 ESC/EAS guidelines (9). Initial follow-up will take place in 2 months to assess the efficacy of their treatment. Patients who are not at the goal LDL-cholesterol will be prescribed 30mg atorvastatin nightly as a 30 tablets supply with five patient-initiated re-fills for 30 tablets each, with final follow-up after 6 additional months. Patients who are at goal on the red yeast rice extract will be recommended to switch to lovastatin 20mg nightly as a bio-identical substitute, but they will be excluded from further analysis.

In both groups, statin adherence will be assessed by pharmacy refill records at the final follow-up. A short, four question questionnaire (Appendix A) will be administered at this point as well. Final follow-up laboratory variables collected will include total cholesterol, HDL, LDL, triglycerides, AST, ALT, creatine kinase, and vitamin D levels.

Conversation guidelines for each clinical encounter in the intervention group are included in Appendix B.

Randomisation

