5.3. Exclusion criteria

1. Dementia
2. Severe Mental Illness
3. History of statin intolerance
4. High-risk for ASCVD
5. Currently on lipid lowering therapy
6. Currently taking red yeast rice extract
7. Pregnant or breast feeding
8. Concomitant use of the following drugs: anti-retroviral therapy, niacin, calcineurin inhibitors, mTOR inhibitors, amiodarone, and fibrates

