6.1. Definitions

The following definitions will be employed in this study.

Statin intolerance

Development of an increase in creatine kinase OR AST/ALT elevation > 3x upper limit of normal OR rhabdomyolysis with statin initiation during the study period.

History of statin intolerance

History of an increase in creatine kinase OR AST/ALT elevation > 3x upper limit of normal OR rhabdomyolysis with statin initiation, prior to enrollment in this study

Moderate risk for ASCVD

7.5%-20% 10-year ASCVD risk by the Pooled Cohorts Equation

Severe Mental Illness

History of schizophrenia or another mental illness with psychotic features

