Appendix B

Clinical Encounter Conversation Guidelines

Control Group Initial Encounter

Point(s) to discuss

1. Acknowledge the patient's reluctance to start statin therapy
2. Reassure the patient that long term data supports the safety of statins
3. Reassure the patient that long term data supports the efficacy of statins

Sample Conversation(s):

"I understand that you are hesitant to start statin therapy. We over two decades of long-term follow-up data regarding statin use. The data clearly shows that statins are extremely safe and patients who stay on statins live longer and healthier lives."

Intervention Group Initial Encounter

Point(s) to discuss

1. Acknowledge the patient's reluctance to start statin therapy

2. ESC/EAS 2019 guidelines recommend an LDL-cholesterol < 2.6 mmol/L (100 mg/dL)
3. Present the option of a natural supplement as an open-ended question
4. The impact of the therapy will be assessed in two months

Sample Conversation(s):

“I understand that you are hesitant to start statin therapy. According to European guidelines, your LDL-cholesterol should be less than 2.6 mmol/L (100 mg/dL) to reduce your risk of a cardiovascular event. What is your opinion on trying a natural supplement to reduce your cholesterol?”

If the patient agrees to red yeast rice extract

“Let's follow up in two months to see if our LDL-cholesterol goals have been met”

Intervention Group Initial Follow-up

If LDL-cholesterol > 2.6 mmol/L (100 mg/dL)

Point(s) to discuss

1. Since the natural remedy did not work, we should switch to the statin to reduce cardiovascular events

Sample Conversation(s):

“Unfortunately, we were not able to meet our goals with the natural supplement. Because of this, let's try the prescription medicine instead (atorvastatin 30mg nightly)”

If LDL-cholesterol < 2.6 mmol/L (100 mg/dL)

Point(s) to discuss

1. The natural remedy did reduce your LDL-cholesterol to our original goal
2. However, the effect of the natural remedy is unreliable over time due to lack of regulation

3. Let's switch to a bio-identical prescription medicine for reliability

“Congratulations, we were able to meet our goal using a natural supplement. This supplement contains naturally occurring lovastatin; however it is difficult to predict the dose that you are receiving since supplements are not regulated. Let's try a medium dose of lovastatin instead (20mg lovastatin nightly)”

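### Entry sets no LDL level, so an intervention patient already below 2.6 mmol/L at baseline can be dropped as at goal at 2 months, while the same patient in the control arm is kept

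*Protocol*

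**What the plan says.** **Entry.** Protocol section 5.2 lists three criteria: age over 40, "Moderate ASCVD risk", and declining a statin. Section 6.1 defines moderate risk as "7.5%-20% 10-year ASCVD risk by the Pooled Cohorts Equation". The summary in section 1.1 describes the same population, "patients with a moderate 10-year ASCVD risk who decline statin therapy". The lipid-related exclusions in section 5.3 concern treatments, for example "Currently on lipid lowering therapy", and not an LDL value.

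**The 2-month test.** Section 4.2 sets the goal in the intervention arm as an absolute LDL below 2.6 mmol/L (100 mg/dL). It then says "Patients who are at goal on the red yeast rice extract will be recommended to switch to lovastatin 20mg nightly", and takes these patients out of the analysis from that point. The summary in section 1.1 words the goal differently, as "a goal of either LDL-C reduction of at least 50% or an LDL-C < 100 mg/dl". Appendix B tells a patient at goal: "The natural remedy did reduce your LDL-cholesterol to our original goal".

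**Control arm.** Sections 4.2 and 7 give controls one follow-up visit, at 6 months. They have no 2-month LDL check and no LDL-based exclusion.

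**Baseline data.** Section 4.2 lists LDL among the baseline laboratory variables, without limiting this to one arm.

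**The concern.** The exclusion appears meant for patients whom the supplement brings to goal. Section 4.5 speaks of attaining the threshold on the extract, and Appendix B credits the remedy with the fall. The rule as written looks only at the 2-month value. It never asks whether LDL was above 2.6 mmol/L beforehand, and entry does not ensure that it was.

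A characteristic present before allocation can therefore trigger an exclusion after allocation, in one arm only. Patients with low baseline LDL are thinned out of the intervention arm and stay in the control arm. If such patients refill statins more or less often than others, the comparison of refill counts carries a difference that the intervention did not cause. For these patients the Appendix B wording would also credit the supplement with a result that it need not have produced.

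**Working it through.** **1. Can a patient enter below the goal?** Yes. A Pooled Cohorts risk of 7.5%-20% is a score and not an LDL floor, and nothing in sections 5.2 or 5.3 adds one.

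**2. Follow that patient through each arm.**

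| Step | Intervention, takes red yeast rice | Control |
|---|---|---|
| Baseline LDL < 2.6 mmol/L | enrolled | enrolled |
| 2 months | LDL compared with 2.6 mmol/L; may be below it with no supplement effect | no visit |
| Analysis | left out if below | kept |

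The summary's either/or goal does not change this, because anyone below 100 mg/dL at entry already meets its second branch.

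**3. How many patients?** Removed = 150 × p × u × r, where p is the share below goal at entry, u the share of those who take the supplement, and r the share of those still below goal at 2 months. The protocol gives none of the three. With p assumed at 10-30% and u = r = 1:
- 150 × 0.10 = 15
- 150 × 0.30 = 45

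Since u and r cannot exceed 1, these are upper bounds for that p. Section 1.1 offers atorvastatin as the alternative and Appendix B puts the supplement as an open question, so u may well be below 1. Controls removed under this rule: 0.

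**4. The plan's own sample size, and whether power is the issue.** Section 4.5 gives a 5-point effect, SD 10, alpha 0.05, power 0.9, 1:1 and a total of 138. Per arm, n = 2(z_α + z_β)²(SD/δ)².
- One-sided: 2 × (1.645 + 1.282)² × (10/5)² = 68.5, so 69 per arm and 138 in total. This reproduces the plan.
- Two-sided: 85 per arm, 170 in total. This does not.

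With 150 controls against 150 - 45 = 105 intervention patients, power for 5 points is 0.989 one-sided and 0.976 two-sided, before dropout. Power is not the problem.

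**5. What bias could follow?** Let b be the share of the intervention arm removed this way, and D the mean compliance of kept minus removed patients. The full-arm mean is (1 - b) × kept + b × removed, so the kept mean differs from it by b × D. With no true effect, SD 10 and 150(1 - b) against 150 analysed, for positive D:

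| b (assumed) | D (assumed, points) | Bias b × D (points) | False-positive rate, one-sided / two-sided |
|---|---|---|---|
| 5% | 5 | 0.25 | 0.076 / 0.055 |
| 10% | 5 | 0.5 | 0.111 / 0.071 |
| 10% | 10 | 1.0 | 0.211 / 0.135 |
| 20% | 10 | 2.0 | 0.495 / 0.372 |
| 30% | 10 | 3.0 | 0.762 / 0.655 |

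The last row is 3.0/5 = 60% of the target effect. Both b and D are assumed. If D is negative the bias runs against the intervention, and if D is zero there is none.

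**The case against.** **The effect on the primary endpoint is not shown.** The endpoint is a refill count, not LDL. A baseline LDL difference matters only if LDL, or something tied to it, predicts refills, and the protocol does not say that it does. This stands. A reader might infer from the table that the result will be biased by up to 3 points; the documents support only that it could be, in either direction.

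**The count is a ceiling.** A reader might take 15-45 as the expected loss. It requires every intervention patient below goal to take the supplement and stay below goal. The protocol makes the supplement a choice, and section 4.2 excludes only those at goal while on it. For the same reason the text does not support saying that patients are removed whether or not they took it; how non-takers are handled is not stated.

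**Numbers were allowed for.** Section 4.5 plans 300 against 138 and names this exclusion. That answers the loss of patients but not the loss of comparability.

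**Baseline LDL may be used elsewhere.** Covariate adjustment commonly sits in an analysis plan, which is not at hand. The protocol supports only the statement that baseline LDL has no role in entry or in the 2-month exclusion.

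**This is one slice of a larger problem.** Any intervention patient at goal on the supplement is dropped, including those it truly helped. That is correct. The slice still merits its own change: its control counterparts can be identified from baseline LDL, while the control counterparts of true responders cannot.

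**Conclusion.** The point holds as a flaw of structure. With no LDL level at entry, an absolute 2-month test that ignores baseline, and exclusion in one arm only, the analysed arms differ in baseline LDL by construction whenever patients below 2.6 mmol/L are enrolled and take the supplement. At an assumed 10-30% below goal, at most 15-45 of 150 intervention patients are affected, against 0 controls under this rule. The size and direction of any bias in compliance cannot be derived from the protocol, and power is not materially affected. It is worth correcting because the mechanism is plain and the remedy uses data already collected.

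**What to change.** Apply the protocol's own 2.6 mmol/L threshold to baseline LDL before allocation, alike in both arms, in one of two ways:
- **Eligibility:** add to section 5.2 that baseline LDL, measured before allocation, is not below 2.6 mmol/L.
- **Analysis set:** keep entry as it is, and restrict the primary analysis in both arms to patients whose baseline LDL is not below 2.6 mmol/L.

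The two wordings of the LDL goal in sections 1.1 and 4.2 must be reconciled at the same time.

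**Cost.** One sentence, and a somewhat smaller recruitment pool or analysis set. Under the second option and the same assumed 10-30%, 30-90 of 300 patients would be set aside, leaving 210-270. That is above both 138 and 170, before dropout and other exclusions. Either option narrows the population, which section 1.1 defines by risk and statin refusal alone.

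**What remains.** Patients brought to goal by the supplement would still be left out of one arm only. That needs a separate change: analysing all allocated patients. It also requires an endpoint definition for those directed to lovastatin, because section 1.1 counts compliance from the start of atorvastatin.

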5.3. Exclusion criteria

1. Dementia
2. Severe Mental Illness
3. History of statin intolerance
4. High-risk for ASCVD
5. Currently on lipid lowering therapy
6. Currently taking red yeast rice extract
7. Pregnant or breast feeding
8. Concomitant use of the following drugs: anti-retroviral therapy, niacin, calcineurin inhibitors, mTOR inhibitors, amiodarone, and fibrates

5.4. Withdrawal criteria

Patients will be able to withdraw from the study at any time at their request.

Patient who develop statin intolerance will be withdrawn from the study.

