4.5. Sample size/Power calculation

This study is designed as a superiority trial. Based on prior literature, we estimate a 50% statin compliance rate with a standard deviation of 10% (2). We will set the minimal detectable effect at a 5% increase in statin compliance, with an $\alpha < 0.05$ and power of 0.9. Based on case-to-control ratio of 1:1, our total minimum sample size for the primary endpoint is 138. However, we will plan on a total sample size of 300 patients, to account for patients who drop out of the study as well as patients who will be excluded due to attaining an LDL-cholesterol of <2.6 mmol/L (100 mg/dL) on red yeast rice extract.

5. Participant entry

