9.2. Consent

Consent to enter the study must be sought from each participant only after a full explanation has been given, an information leaflet offered and time allowed for consideration. Signed participant consent should be obtained. The right of the participant to refuse to participate without giving reasons must be respected. After the participant has entered the study the clinician remains free to give alternative treatment to that specified in the protocol at any stage if he/she feels it is in the participant's best interest, but the reasons for doing so should be recorded. In these cases the participants remain within the study for the purposes of follow-up and data analysis. All participants are free to withdraw at any time from the protocol treatment without giving reasons and without prejudicing further treatment.

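### Sections 5.4 and 9.2 do not separate stopping treatment from leaving the study, so patients can drop out of a compliance endpoint because they stopped complying

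*Protocol*

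**What the plan says.** - Section 5.4 (Withdrawal criteria): "Patients will be able to withdraw from the study at any time at their request". It does not say whether stopping the tablets or missing a visit counts as such a request.
- Section 9.2 (Consent): "All participants are free to withdraw at any time from the protocol treatment without giving reasons". The sentence before it, which keeps participants in follow-up and analysis, refers to patients whose clinician gives them alternative treatment.
- Section 4.5 (Sample size): the minimum for the primary endpoint is 138 in total. It is raised to 300 "to account for patients who drop out of the study as well as patients who will be excluded" for reaching the LDL-cholesterol goal on red yeast rice extract. Neither group is given a rate.
- Section 4.2 (Study protocol): "statin adherence will be assessed by pharmacy refill records at the final follow-up". Section 7 puts that visit at 6 months for controls and 8 months for the intervention group, which also has a 2-month visit.
- Section 4.3 (Outcome measures): each patient scores 0 to 6 by number of refills.
- Section 5.2 (Inclusion criteria): the trial enrols people who decline statin therapy.

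**The concern.** In most trials a patient who leaves has an unknown outcome. Here, leaving is often the outcome. A statin-reluctant patient who says they no longer want the tablets is showing low compliance, and pharmacy records would show it without a visit.

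A site that reads the request as withdrawal from the study may stop collecting data. A site that reads it as withdrawal from treatment would go on to read the refill record. The protocol does not say which applies, and 4.5 already budgets for drop-outs as lost. The loss is then informative: those removed are mainly those who fill least. The arms also have different schedules (one follow-up visit over 6 months against two over 8 months), so equal loss cannot be taken for granted. The comparison could be shifted in either direction.

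**Working it through.** **1. The plan's own figure.** Inputs from 4.5: difference 5 points, SD 10 points, power 0.90, alpha 0.05, ratio 1:1. Sidedness is not stated.
- Formula: n per arm = 2(z_alpha + z_power)² × SD² / difference².
- One-sided: 2 × (1.645 + 1.282)² × 100/25 = 68.5, so 69 per arm and 138 in total. This reproduces the plan.
- Two-sided: 2 × (1.960 + 1.282)² × 100/25 = 84.1, so 85 per arm and 170 in total.
- Allowance for drop-out and LDL-goal exclusion together: (300 − 138)/300 = 54%, or (300 − 170)/300 = 43% against the two-sided figure.

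The allowance is large, but it protects power only. It does nothing against bias from who is lost.

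**2. What removal does to an arm's mean.** Let m be the true mean compliance of all randomised patients in the arm (fills as a percentage of six), d the share who withdraw and are removed, and f the withdrawers' own compliance. The patients left average (m − d × f)/(1 − d). The protocol gives neither d nor f, so every value of them below is an assumption.

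**3. No true effect** (m = 50 in both arms, the rate in 4.5; f = 10 assumed).
- d = 10%: (50 − 1)/0.90 = 54.4
- d = 15%: (50 − 1.5)/0.85 = 57.1
- d = 20%: (50 − 2)/0.80 = 60.0

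With 10% removed in controls, the false difference is 60.0 − 54.4 = 5.6 points if 20% are removed in the intervention arm, and 57.1 − 54.4 = 2.6 points (unrounded inputs) if 15% are. If the rates are exchanged between arms, the sign reverses.

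**4. True 5-point effect** (m = 50 control, 55 intervention; f = 1 of 6 fills = 16.7 assumed).

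| Removed, control / intervention | Control mean | Intervention mean | Difference |
|---|---|---|---|
| 10% / 10% | 53.7 | 59.3 | 5.6 |
| 20% / 20% | 58.3 | 64.6 | 6.25 |
| 20% / 15% | 58.3 | 61.8 | 3.4 |
| 20% / 10% | 58.3 | 59.3 | 0.9 |
| 30% / 20% | 64.3 | 64.6 | 0.3 |
| 10% / 20% | 53.7 | 64.6 | 10.9 |

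With equal removal and equal f the difference becomes 5/(1 − d), so equal drop-out is harmless only when there is no true effect.

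**5. Effect acting only through stopping** (assumed: patients who stay fill 60% in both arms, withdrawers 16.7%; 30% stop in controls, 18.46% in the intervention arm).
- Control: 60 − 0.30 × 43.3 = 47.0
- Intervention: 60 − 0.1846 × 43.3 = 52.0
- True difference 5.0; difference among those kept 60 − 60 = 0

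If autonomy works by preventing stopping, removing those who stop erases the effect under test.

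**The case against.** A reader might infer that 5.4 and 9.2 contradict each other. They do not. Each grants a permission, and a right to leave the study can coexist with a right to leave treatment. Section 5.4 does not say that stopping tablets is leaving the study.

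A reader might also infer that the protocol orders patients who stop to be discarded. It does not. Enlarging a trial for drop-out is ordinary, and 4.5 uses exclusion wording only for the LDL-goal group. Section 4.2 fixes when records are assessed and does not make attendance a condition. The 0 to 6 scale can already score a patient who stops refilling without formally withdrawing.

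Nor does 9.2 already settle the matter by keeping patients who stop in the analysis. Its retention sentence covers clinician-given alternative treatment and helps only by analogy.

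These points stand, as does the fact that the size rests on assumed drop-out. An extra visit does not establish that the intervention arm loses twice as many.

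The remaining objection is that the scoring of withdrawn patients belongs in the SAP, which is not shown. That is right for the analysis rule. However, an SAP cannot recover refill records that a site stopped collecting or had no consent to read. Withdrawal status and consent are fixed in the protocol, and that part of the concern survives.

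**Conclusion.** The concern holds as an undefined boundary that permits avoidable, outcome-dependent loss from the primary endpoint. It concerns patients who ask to stop and are recorded as off study. It does not reach patients who merely stop refilling, and the separate statin-intolerance rule in 5.4 is not part of it.

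Under the assumed inputs the distortion ranges from a false 5.6 points where there is no effect to the near or complete loss of a true 5-point effect. These are illustrations, not estimates, since the protocol states no drop-out rate, no difference by arm and no fill rate among drop-outs. They show that plausible losses can match the effect the trial is designed to detect. The sample size of 138 is not disputed by this point. The change is cheap and worth making before patients leave, because consent to read later records is hard to obtain afterwards.

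**What to change.** 1. In 5.4 and 9.2, distinguish stopping protocol treatment or missing visits from withdrawing consent to data use. Have the consent cover reading refill records after visits stop.
2. Obtain refill records over the full 6-month window for every patient who was prescribed atorvastatin and has not refused data use. Enter the observed fills, including 0, in the primary analysis.
3. State in advance how to handle intervention patients on red yeast rice who leave before the 2-month visit. They never had an atorvastatin prescription or a refill window, so neither a score of 0 nor a missing value is self-evident. Add a sensitivity analysis under the alternative scoring.
4. If the Appendix A questions are asked early, reword the recall period, now 6 months on atorvastatin, to the time actually on treatment.
5. In 4.5, limit the drop-out allowance to true loss of refill data.

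The cost is protocol and consent wording and a few more requests for records the trial already plans to read. Observed compliance will be lower than among patients who stay, and will describe the patients randomised more faithfully.

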Appendix A Final Follow-up questionnaire

Have you had any of the following symptoms from atorvastatin over the past 6 months?			
Myalgias (muscle aches)	 Yes	 No	 Not Sure
Fatigue	 Yes	 No	 Not Sure
Mental fog (slow thinking or memory issues)	 Yes	 No	 Not Sure
Gastrointestinal upset	 Yes	 No	 Not Sure

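### Section 5.4 removes patients with statin intolerance from the study, so those found before final follow-up have no planned endpoint assessment, while section 9.2 keeps switched patients in follow-up and analysis

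*Protocol*

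**What the plan says.** Protocol section 5.4 has two rules. Patients may leave at their own request, and: "Patient who develop statin intolerance will be withdrawn from the study". Section 6.1 defines intolerance by creatine kinase, AST/ALT or rhabdomyolysis findings that arise with statin initiation during the study.

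Section 9.2 lets the clinician depart from the protocol treatment and says of such patients: "In these cases the participants remain within the study for the purposes of follow-up and data analysis". It also speaks of participants withdrawing from protocol treatment, so the protocol does separate leaving treatment from leaving the study.

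Section 4.2 fixes when the endpoints are assessed. For the primary endpoint: "In both groups, statin adherence will be assessed by pharmacy refill records at the final follow-up". For perceived side effects: "A short, four question questionnaire (Appendix A) will be administered at this point as well". Final follow-up is at 6 months in the control arm and 8 months in the intervention arm. The intervention arm's earlier visit has a narrower purpose: "Initial follow-up will take place in 2 months to assess the efficacy of their treatment". After baseline, the enzymes that define intolerance are named only at the end: "Final follow-up laboratory variables collected will include total cholesterol, HDL, LDL, triglycerides, AST, ALT, creatine kinase, and vitamin D levels".

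Both endpoints are tied to atorvastatin. Section 1.1 states: "The primary endpoint will be 6-month compliance of statin therapy, after the initiation of atorvastatin". The Appendix A questionnaire asks: "Have you had any of the following symptoms from atorvastatin over the past 6 months".

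**The concern.** Intolerance as defined in 6.1 occurs after allocation and is related to treatment. A rule that ends participation when it occurs makes missing outcomes depend on how the patient responded to the drug, and this can bias both endpoints. The secondary endpoint is the more exposed, because patients with a documented reaction may leave before anyone asks what side effects they perceived.

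The arms may also lose patients at different rates. The intervention arm is followed two months longer and has an extra visit, so there is more opportunity to notice intolerance. Section 1.1 describes red yeast rice extract as a natural form of statin, but 6.1 does not say whether starting it counts as statin initiation. If it does, the intervention arm can lose patients before the primary endpoint's six months begin.

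An intolerant patient who is then given another treatment meets 5.4 (out of the study) and 9.2 (kept in follow-up and analysis). Nothing says which prevails.

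**Working it through.** **Reading the rules together**

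| Situation | 5.4 | 9.2 | Endpoint data under 4.2 |
|---|---|---|---|
| Intolerance found before final follow-up, not switched | Leaves the study | Not engaged | No planned refill assessment or questionnaire |
| Intolerance found before final follow-up, switched | Leaves the study | Stays in follow-up and analysis | Depends on which rule prevails |
| Intolerance first found in the final laboratory tests | Leaves the study | Not engaged unless switched | Due at the same visit; 5.4 does not say whether the data are kept |
| Intolerance on red yeast rice, before atorvastatin | Unclear: depends on the meaning of statin initiation in 6.1 | Applies if switched | Neither endpoint fits as written |

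**Scale of the plan's own figure.** Section 4.5 gives mean compliance 50%, SD 10%, a 5% increase, alpha 0.05, power 0.9 and a total of 138. With a one-sided test, n per arm = 2 × (1.645 + 1.282)² × 10² / 5² = 68.5, rounded up to 69, so 138 in total. The stated figure is reproduced, and the 5% is an absolute difference in mean compliance. (A two-sided test gives 85 per arm, 170 in total.) The design target for comparison is therefore 5 points.

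**Illustration.** The protocol gives no intolerance rate. All of the following are assumptions: fraction of an arm lost, w = 2% to 5% (150 × 0.02 = 3; 150 × 0.05 = 7.5 patients); mean compliance of those lost, c = 20% or 80%; true side-effect rate 20%.

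*One arm's mean compliance, true mean 50%:* observed = (0.50 − c·w)/(1 − w)

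- c = 20%, w = 2%: (0.50 − 0.004)/0.98 = 50.61%
- c = 20%, w = 5%: (0.50 − 0.010)/0.95 = 51.58%
- c = 80%, w = 2%: (0.50 − 0.016)/0.98 = 49.39%
- c = 80%, w = 5%: (0.50 − 0.040)/0.95 = 48.42%

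The arm mean shifts by 0.61 to 1.58 points, up or down.

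*Difference between arms, same c in both:*

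- No true difference, equal w: 0 points.
- No true difference, w = 2% against 5%: 51.58 − 50.61 = 0.97 points at c = 20%. At c = 80% the size is the same with the opposite sign.
- True 50% against 55%, equal w: 5/(1 − w) = 5.10 points at 2% and 5.26 at 5%, instead of 5.00.
- True 50% against 55%, 5% lost in control and 2% in intervention, c = 10%: (55 − 0.2)/0.98 − (50 − 0.5)/0.95 = 55.92 − 52.11 = 3.81 points. With c = 25%: 55.61 − 51.32 = 4.30 points (rounded from unrounded values).

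*Side-effect rate, true 20%, share p of those lost who would report symptoms:* observed = (0.20 − p·w)/(1 − w)

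- p = 0: 20.41% (w = 2%), 21.05% (w = 5%)
- p = 20%: 20.00% at either w
- p = 50%: 19.39% (w = 2%), 18.42% (w = 5%)

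The direction is open for both endpoints. Those lost may have been poor or regular takers. Section 6.1 has no symptom item beyond what rhabdomyolysis may imply, so they may report symptoms more or less often than others.

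**The case against.** The strongest reply has four parts.

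1. *A specific rule normally overrides a general one.* Section 5.4 may be an exception to 9.2. That reading is fair and would settle the conflict, but it would also confirm that these patients leave before their outcomes are taken.

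2. *The loss hardly arises on the planned schedule.* Creatine kinase and AST/ALT are named after baseline only at final follow-up, when refills and questionnaire are collected anyway. Earlier cases would come mainly from unscheduled tests or clinical presentation. This stands and limits the reach.

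3. *The primary endpoint may survive, and its analysis belongs to the statistical analysis plan.* Refill records exist without a visit, and 5.4 does not say data are discarded. This stands for the refill count. It does not cover the questionnaire: 5.4 is a rule of conduct, and no analysis plan can recover answers that were never sought.

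4. *The illustration has no anchor.* True: the inputs are assumed, nothing supports 2-5% for early detection, and the analysed intervention arm will be smaller than 150 because patients at LDL goal are excluded. The percentages do not depend on arm size, but the patient counts do. The 80% case is unlikely for anyone who stops early; it describes patients found late or who keep refilling. Equal loss barely moves the difference.

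The points about 6.1 and red yeast rice are secondary. They matter here because they decide whom 5.4 affects.

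**Conclusion.** The concern holds. Followed as written, 5.4 takes patients out of the study on a treatment-related event after allocation, before the only planned assessment of either endpoint. It also conflicts with 9.2 for those who are switched, unless it is read as an exception. The certain harm is to the perceived side-effect endpoint; the primary endpoint is at risk only if refill records are not retrieved.

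The size cannot be derived from the protocol and may be small. On the assumed inputs above, equal loss changes a true 5-point difference by at most about 0.3 points. Unequal loss of 2% against 5% changes the difference by about 1 point in either direction. This should be corrected, but it does not by itself undermine the trial.

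**What to change.** - Reconcile 5.4 with 9.2 so that intolerance is recorded as an event and does not by itself end study participation.
- For patients who had started atorvastatin, still collect refill records and give the Appendix A questionnaire at the planned final follow-up, and analyse them in their allocated arm. Say that this includes patients first detected in the final laboratory tests.
- For patients who become intolerant on red yeast rice before atorvastatin, keep them in follow-up and state how they count, since neither endpoint fits them as written.
- State in 6.1 whether statin initiation includes red yeast rice, and reconcile the wording on whether the threefold limit covers AST/ALT only or creatine kinase as well. No threshold is proposed here.

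Whether treatment stops remains a clinical decision and is untouched. The cost is wording in 5.4, 6.1 and 9.2, one counting rule, and a small amount of added follow-up for the patients concerned.
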